5.3. Randomization Criteria

Participants must meet all [inclusion/exclusion criteria](#) as well as all criteria for concomitant medications (including stability criteria) at time of randomization.

5.4. Lifestyle Considerations

5.4.1. Contraception

The investigator (or his or her designee), in consultation with the participant, will confirm that the participant has selected an appropriate method of highly effective contraception for the individual participant and his or her partner(s) from the permitted list of contraception methods (see [Appendix 4, Section 10.4.4](#)), and will confirm that the participant has been instructed in its consistent and correct use. At time points indicated in the [SoA](#), the investigator or designee will inform the participant of the need to use highly effective contraception consistently and correctly, and document the conversation and the participant's affirmation in the participant's chart (participants need to affirm their consistent and correct use of at least 1 of the selected methods of contraception). In addition, the investigator or designee will instruct the participant to call immediately if the selected contraception method is discontinued or if pregnancy is known or suspected in the participant or partner.

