10.4.2. Female Participant Reproductive Inclusion Criteria

A female participant is eligible to participate if she is not pregnant or breastfeeding, and at least 1 of the following conditions applies:

- Is not a WOCBP (see definitions below in [Section 10.4.3](#)).

OR

- Is a WOCBP and using a contraceptive method that is highly effective (with a failure rate of <1% per year), preferably with low user dependency, as described below during the intervention period and for at least 28 days after the last dose of study intervention, which corresponds to the time needed to eliminate any study intervention(s). If the primary form of contraception is an estrogen containing hormone method, then the women or her partner must additionally use a barrier method. The investigator should evaluate the effectiveness of the contraceptive method in relationship to the first dose of study intervention. The investigator is responsible for review of medical history, menstrual history, and recent sexual activity to decrease the risk for inclusion of a woman with an early undetected pregnancy. A barrier method must be used with all highly effective methods that are user dependent listed below. Participants enrolled in Canadian sites must use at least 2 forms of contraception regardless of the user dependency of the method(s),

including at least 1 form of highly effective contraception and 1 form of effective contraception.

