10.4.4. Contraception Methods

Highly Effective Methods That Have Low User Dependency

1. Implantable progestogen-only hormone contraception associated with inhibition of ovulation and a barrier method.
2. Intrauterine device (IUD).
3. Intrauterine hormone-releasing system (IUS).
4. Bilateral tubal occlusion.
5. Vasectomized partner.
 - Vasectomized partner is a highly effective contraceptive method provided that the partner is the sole sexual partner of the WOCBP and the absence of sperm has been confirmed. If not, an additional highly effective method of contraception should be used. The spermatogenesis cycle is approximately 90 days.

Highly Effective Methods That Are User Dependent

1. Combined (estrogen- and progestogen-containing) hormonal contraception associated with inhibition of ovulation and a barrier method if using hormonal contraceptive agent:
 - oral;
 - intravaginal;
 - transdermal.
2. Progestogen-only hormone contraception associated with inhibition of ovulation and a barrier method:
 - oral;
 - injectable.
3. Sexual abstinence:
 - Sexual abstinence is considered a highly effective method only if defined as refraining from heterosexual intercourse during the entire period of risk associated with the study intervention. The reliability of sexual abstinence needs to be evaluated in relation to the duration of the study and the preferred and usual lifestyle of the participant. If during the study the subject decides to become

sexually active they must inform the study site and start using one of the effective contraception method described in this section.

Effective methods to be used with all highly effective contraceptive methods that are user dependent listed above:

4. Male or female condom with or without spermicide.
5. Cervical cap, diaphragm, or sponge with spermicide.

Collection of Pregnancy Information

For both unapproved/unlicensed products and for marketed products, an exposure during pregnancy (EDP) occurs if:

- A female becomes, or is found to be, pregnant either while receiving or having been exposed (eg, because of treatment or environmental exposure) to the investigational product; or the female becomes or is found to be pregnant after discontinuing and/or being exposed to the investigational product;
- An example of environmental exposure would be a case involving direct contact with a Pfizer product in a pregnant woman (eg, a nurse reports that she is pregnant and has been exposed to chemotherapeutic products).

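### The visit affirmation in Protocol 5.4.1 does not verify the Canadian two-form contraception rule, and Appendix 4 is inconsistent on the class of method required after abstinence ends

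*Protocol*

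**What the plan says.** Section 5.4.1 has the investigator confirm that a suitable highly effective method has been chosen from the list in Appendix 4. At the time points in the Schedule of Activities, site staff "will inform the participant of the need to use highly effective contraception consistently and correctly" and document the participant's affirmation. A parenthesis sets the content of that affirmation: "participants need to affirm their consistent and correct use of at least 1 of the selected methods of contraception". The Schedule places a contraception check at all ten scheduled visits and at early withdrawal.

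Appendix 4, 10.4.2, sets the requirement for women. The base condition is that the participant "Is a WOCBP and using a contraceptive method that is highly effective (with a failure rate of <1% per year"). Three additions follow:

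- "A barrier method must be used with all highly effective methods that are user dependent listed below".
- "If the primary form of contraception is an estrogen containing hormone method, then the women or her partner must additionally use a barrier method".
- "Participants enrolled in Canadian sites must use at least 2 forms of contraception regardless of the user dependency of the method(s"), with one form from the highly effective class and one from the effective class.

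Section 10.4.4 lists the methods. Under sexual abstinence it says that a participant who decides to become "sexually active they must inform the study site and start using one of the effective contraception method described in this section". The barrier methods (condom, cap, diaphragm, sponge) then appear under their own heading: "Effective methods to be used with all highly effective contraceptive methods that are user dependent listed above".

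**The concern.** An affirmation that is complete once one method is named cannot show that two are in use. Where Appendix 4 demands two, a participant who has dropped one of them may be able to give the affirmation truthfully, and the visit record would look complete. The amendment history adds context: the Canadian rule was introduced at the national regulator's request, in Appendix 4 only, and the current 5.4.1 contains no matching check.

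The abstinence sentence raises a different problem. It applies mid-trial, while dosing continues, and it names the class of method in a word that the same section reserves for accompaniments to highly effective methods. A site following it literally and a site following 10.4.2 could give different instructions.

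What is at stake is the consistency of a safety check. Section 2.2.4 ties the nonclinical support for including women of childbearing potential to the use of appropriate contraception, and Section 8.11 makes refusal of appropriate contraception a ground for permanent withdrawal. Both depend on sites knowing what to verify.

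**Working it through.** No arithmetic applies and the plan gives no figure to reproduce. The check sets the requirement beside the affirmation, case by case, for women of childbearing potential.

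| Case | Appendix 4 requires | 5.4.1 affirmation secures | Result |
|---|---|---|---|
| Outside Canada: IUD, IUS, bilateral tubal occlusion, or vasectomized partner meeting the stated conditions | One method; no barrier listed | At least one | Matches |
| Outside Canada: hormonal user-dependent methods, or progestogen implant | Method plus barrier | At least one | Depends on whether the barrier is part of the selected method |
| Canada: IUD, IUS, tubal occlusion or vasectomized partner | Two forms: one highly effective, one effective | At least one | Falls short |
| Canada: hormonal methods or implant | Two forms: one highly effective, one effective | At least one | Depends on the same reading |

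**Third row.** This is the clear gap. The listed entry carries no barrier, so the second form comes only from the Canadian sentence in 10.4.2. A participant using an IUD who has stopped the second form can affirm the IUD and satisfy 5.4.1 as written.

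**Second and fourth rows.** Section 10.4.4 writes the barrier into the numbered hormonal entries and into the implant entry. If the selected method means the whole entry, affirming it affirms both parts. If the plural in 5.4.1 means each component counts separately, one component is enough, and the parenthesis does not say which. The text does not settle this.

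**Comparison within the protocol.** Appendix 13 words the check differently. For telehealth visits (10.13.1) and for local or home testing (10.13.2), staff confirm adherence to whatever method or methods the protocol demands. That wording adapts to the participant and has no one-method floor, so the remote check is worded more completely than the in-clinic affirmation.

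**Abstinence.** Three statements bear on the class of method:

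1. 5.4.1 and 10.4.2 call for a highly effective method.
2. The abstinence paragraph of 10.4.4 calls for an effective one.
3. 10.4.4 uses the latter term as the heading for barriers that accompany highly effective user-dependent methods, and the Canadian sentence in 10.4.2 also treats the two terms as separate classes.

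If the terms carry the meaning that Appendix 4 gives them, statement 2 can be met by a barrier alone, which contradicts statement 1. This conflict involves Appendix 4's own text and does not arise from the visit check.

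**The case against.** The best defence is that 5.4.1 speaks of selecting a highly effective method from 10.4.4, and that the hormonal entries there already contain the barrier. On that reading a participant who dropped the barrier could not honestly affirm her selected method, and a barrier by itself would not count. This is a fair reading, and it removes most of the difficulty for hormonal methods. It does not help Canadian participants whose listed method carries no barrier.

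On abstinence, the word may be loose drafting for any method in the section, most of which are highly effective. That is plausible. It makes the sentence an ambiguity rather than a clear permission, but a site has no means of telling which was meant.

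Other controls also exist. Participants are told to call immediately if the selected method is discontinued, pregnancy tests are done at every visit and after a missed cycle, and refusal of appropriate contraception leads to withdrawal. These limit the consequence. They do not replace the check: the call relies on self-report, and a pregnancy test detects a pregnancy, not a dropped method.

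A reader might infer more than the text supports:

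- *That Appendix 4 demands a barrier from everyone.* It is conditional, and four listed options carry none outside Canada.
- *That the two-form rule covers every Canadian participant.* It sits in the female criteria, under the condition for women of childbearing potential; men have a separate rule in 10.4.1.
- *That 5.4.1 waives Appendix 4.* It restates the need for highly effective contraception and governs only what is affirmed and documented.

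**Conclusion.** The point holds as a minor textual inconsistency with a safety bearing. The affirmation in 5.4.1 does not verify the two-form rule for women of childbearing potential at Canadian sites. It does not clearly verify the barrier where one is required elsewhere. On a literal reading, the class of method after abstinence is contradictory.

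The size cannot be stated. The documents do not give the number of Canadian participants, of women of childbearing potential, of users of each method, or of abstinent participants who might change. A reader might conclude that exposure during pregnancy becomes more likely. The documents contain no figure from which to estimate that, and the other controls work against it.

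The conclusion assumes that sites apply 5.4.1 as written, and that the two class names carry the meanings Appendix 4 gives them. If the abstinence sentence was meant loosely, that part is a matter of clarity only; the Canadian gap remains either way.

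**What to change.** Reconcile 5.4.1, 10.4.2 and 10.4.4 in two places:

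- **5.4.1:** word the affirmation so that it covers every method the protocol requires of that participant. The Appendix 13 wording already does this and could be reused. It would take in the Canadian rule without restating it.
- **10.4.4, abstinence paragraph:** state the class of method to be started in terms that agree with 10.4.2 and with the section's own headings.

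Which contraceptive rule should prevail is for the sponsor to decide; the request is only that the sections say the same thing. The cost is about two sentences in the next amendment, plus the same edit in any site material that repeats the wording. No procedure, visit or analysis changes.

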5.5. Screen Failures

Screen failures are defined as participants who consent to participate in the clinical study but are not subsequently randomly assigned to investigational product. A minimal set of screen failure information is required to ensure transparent reporting of screen failure participants to meet the Consolidated Standards of Reporting Trials (CONSORT) publishing requirements and to respond to queries from regulatory authorities. Minimal information includes demography, screen failure details, eligibility criteria, and any serious adverse event (SAE).

Participants who do not have all tests completed within the screening period or who temporarily do not meet study entry criteria for participation in this study (eg, screen failure due to treatment with antibiotics during the screening period, or for administrative reasons) may be re-screened 1 time under a new participant number; the participant's prior ID number and reason for re-screening must be documented.

6. STUDY INTERVENTION

Study intervention is defined as any investigational intervention(s), marketed product(s), placebo, or medical device(s) intended to be administered to a study participant according to the study protocol.

For the purposes of this protocol, the term investigational product may be used synonymously with study intervention.

For this study, the investigational product(s) are PF-06650833, PF-06651600, and tofacitinib administered as individual products, and the combination of PF-06650833 administered together with PF-06651600 and of PF-06650833 coadministered with tofacitinib.

Investigational product will be administered only to participants who have provided informed consent. Once a participant's participation in the study has ended, investigational product will no longer be supplied to the participant by the investigative site and/or sponsor.

6.1. Study Intervention(s) Administered

Intervention Name	PF-06650833/ Tofacitinib/ Placebo for PF-06651600	PF-06650833/ PF-06651600/ Placebo for tofacitinib	PF-06650833/ Placebo for PF-06651600/ Placebo for tofacitinib	Placebo for PF-06650833/ PF-06651600/ Placebo for tofacitinib	Placebo for PF-06650833/ Placebo for PF-06651600/ tofacitinib
ARM	*1	2	3	4	5
Type	Drug				
Dose Formulation	Tablets				
Unit Dose Strength	200 mg/ 11 mg/ 0 mg	200 mg/ 50 mg/ 0 mg	200 mg/ 0 mg/ 0 mg	0 mg/ 50 mg/ 0 mg	0 mg/ 0 mg/ 11 mg
Dosage Level	400 mg QD/ 11 mg QD/ 0 mg QD	400 mg QD/ 100 mg QD/ 0 mg QD	400 mg QD/ 0 mg QD/ 0 mg QD	0 mg QD/ 100 mg QD/ 0 mg QD	0 mg QD/ 0 mg QD/ 11 mg QD
Route of Administration	Oral				
Investigational Medicinal Product (IMP)	IMP				

Sourcing	Provided centrally by the Sponsor
Packaging and Labeling	Study intervention will be provided in blister packs in cartons containing one month of supplies. Each blister pack and carton will be labeled as required per country requirement.
Current Name	tofacitinib is also called Xeljanz®

6.1.1. Administration

Participants will swallow the investigational products whole and will not manipulate or chew the investigational products prior to swallowing. IP will be provided in cartons containing 4 blister cards of IP in individual blisters. A single dose (administration) of IP will consist of 5 tablets provided as a row in a blister card Table 1. The row will contain different tablet types corresponding to the different study drugs and matching placebos. Participants are to take all tablets in 1 row of the blister card each day orally in a fasted state (at least approximately 4 h after the last and approximately 1.5 h before the next meal), but preferably should be taken consistently in the same manner, ideally in the AM before breakfast. Those participants who cannot take the dose in the morning due to work or other regularly occurring issue may take the dose later in the day provided the fasting requirements are met and the doses are taken at approximately the same time each day. Participants will record dosing in a dosing log (diary).

Table 1. Dosing and Administration of Investigational Products

Treatment Arm	Treatment group (QD)	Treatment Assignment (Blister Pack)	Matching Placebo (Blister Pack)	Total Tablets per Day
1	PF-06650833 (400 mg) + tofacitinib (11 mg)	2 x 200 mg PF-06650833 MR tablets AND 1 x 11 mg tofacitinib MR tablet	2 PF-06651600 IR matching placebo tablets	5
2	PF-06650833 (400 mg) + PF-06651600 (100 mg)	2 x 200 mg PF-06650833 MR tablets AND 2 x 50 mg PF-06651600 IR tablets	1 tofacitinib MR matching placebo tablet	5
3	PF-06650833 400 mg	2 x 200 mg PF-06650833 MR tablets	2 PF-06651600 IR and 1 tofacitinib MR matching placebo tablets	5
4	PF-06651600 100 mg	2 x 50 mg PF-06651600 IR tablets	2 PF-06650833 MR and 1 tofacitinib MR matching placebo tablets	5
5	Tofacitinib 11 mg	1 x 11 mg tofacitinib MR tablet	2 PF-06650833 MR and 2 PF-06651600 IR matching placebo tablets	5

6.2. Preparation/Handling/Storage/Accountability

1. The investigator or designee must confirm appropriate temperature conditions have been maintained during transit for all study interventions received and any discrepancies are reported and resolved before use of the study intervention, as applicable for temperature-monitored shipments.
2. Only participants enrolled in the study may receive study intervention and only authorized site staff may supply or administer study intervention. All study interventions must be stored in a secure, environmentally controlled, and monitored (manual or automated recording) area in accordance with the labeled storage conditions with access limited to the investigator and authorized site staff. At a minimum, daily minimum and maximum temperatures for all site storage locations must be documented and available upon request. Data for nonworking days must indicate the minimum and maximum temperature since previously documented for all site storage locations upon return to business.
3. The investigator, institution, or the head of the medical institution (where applicable) is responsible for study intervention accountability, reconciliation, and record maintenance (ie, receipt, reconciliation, and final disposition records). All study interventions will be accounted for using an IP accountability form/record.
4. Further guidance and information for the final disposition of unused study interventions are provided in the IP manual.
5. Any storage conditions stated in the SRSD will be superseded by the storage conditions stated on the product label.
6. Study interventions should be stored in their original containers and in accordance with their labels.
7. See the IP manual, package insert, or equivalent for storage conditions of the study intervention.
8. Site staff will instruct participants on the proper storage requirements for take-home study intervention.
9. Any excursions from the study intervention label storage conditions should be reported to Pfizer upon discovery along with any actions taken. The site should actively pursue options for returning the study intervention to the storage conditions described in the labeling, as soon as possible. Once an excursion is identified, the study intervention must be quarantined and not used until Pfizer provides permission to use the study intervention. It will not be considered a protocol deviation if Pfizer approves the use of the study intervention after the temperature excursion. Use of the study intervention prior to Pfizer approval will be considered a protocol deviation. Specific details regarding the definition of an excursion and information the site should report for each excursion will be provided to the site in the IP Manual.

10. The sponsor or designee will provide guidance on the destruction of unused study intervention (eg, at the site). If destruction is authorized to take place at the investigator site, the investigator must ensure that the materials are destroyed in compliance with applicable environmental regulations, institutional policy, and any special instructions provided by Pfizer, and all destruction must be adequately documented.

Additional details about accountability, storage, destruction, and excursion reporting can be found in the IP Manual.

6.2.1. Preparation and Dispensing

The IP will be provided as 4 weekly blister cards packaged and dispensed in cartons with tamper-evident seals. It will be dispensed using an Interactive Response Technology (IRT) system at each dispensing visit specified in the [SoA](#). A qualified staff member will dispense the IP via the unique container number identified by the IRT system in the cartons provided, in quantities appropriate for the study visit schedule. The participant/caregiver should be instructed to maintain the product in the carton and blister cards provided throughout the course of dosing and return the carton and blister cards to the site at the next study visit.

6.3. Measures to Minimize Bias: Randomization and Blinding

6.3.1. Allocation to Investigational Product

Allocation of participants to treatment groups will proceed through the use of an IRT system. The site personnel (study coordinator or specified designee) will be required to enter or select information including but not limited to their Login Identification (ID) and password, the protocol number, and the Single Subject Identification Number (SSID or Subject ID) assigned by the IRT system. The site personnel will then be provided with a treatment assignment, randomization number, and dispensable unit (DU) or container number when IP is being supplied via the IRT system. The IRT system will provide a confirmation report containing the SSID or Subject ID, randomization number and DU or container number assigned. The confirmation report must be stored in the sites' files.

Investigational product will be dispensed at the study visits summarized in the [SoA](#).

Returned IP must not be redispensed to the participants. The study-specific IRT Quick Reference Guide (QRG) and investigator Site Overview will provide contact information and further details on the use of the IRT system.

